Postoperative Bladder Filling After Outpatient Laparoscopic Hysterectomy and Time to
Discharge: A Randomized Controlled Trial
NCT Number: Not Yet Assigned
Document Date: 12/3/2024

Study Protocol

We will be evaluating the effects of backfilling the bladder on time to void and time to discharge from the post-anesthesia care unit (PACU) in patients undergoing laparoscopic hysterectomy. A randomization scheme using a block size of four will be generated. Sealed randomization envelopes will be opened for each subject after anesthesia is initiated in the operating suite. This study will be single-blinded to the participant. After group allocation, the surgeon will be informed of whether or not the bladder will be backfilled at the completion of the surgery prior to Foley catheter removal. If the patient is assigned to group A, 200 mL of room temperature, sterile normal saline will be instilled retrograde into the bladder at the completion of surgery prior to Foley catheter removal and the Foley subsequently removed intraoperatively. If the patient is assigned to group B, the Foley catheter will be removed intraoperatively at completion of the procedure. Our standard protocol is to use a 16F Foley catheter for gynecologic laparoscopy cases and patients from both groups will receive the same size catheter. Two hundred mL of sterile saline will be chosen as the amount to backfill to prevent postoperative overdistension as the patient will continue to naturally produce urine while in the recovery room awaking from anesthesia.

We used historical controls to determine our time to discharge and then calculated an adequate sample size for our primary outcome, time to discharge, with a clinically relevant 30-minute difference.

Information will be collected about narcotics receiving during the surgical procedure, as this may affect urinary retention rates. In addition, the following information will be collected: patient demographics, such as age, race, ethnicity, insurance status, BMI; health history: medical comorbidities, surgical history, preoperative medications, history of bladder problems, history of neurologic problems, history of chronic pain, and tobacco use; procedure: indication for procedure, benign/malignant pathology, time to discharge, time to void, urine output, need to go home with foley catheter, intraoperative urinary tract injury, intraoperative narcotics administration, surgical complications, estimated blood loss, intraoperative/postoperative IV fluids, postoperative opioid use, and postoperative UTI.

If a subject is unable to void, they will be admitted overnight and observed for repeat trial of voiding.

Adverse events will be monitored and collected through the Day 30 visit, to include the following categories: Death, Life-threatening, Hospitalization (initial or prolonged), Disability or Permanent Damage, Required Intervention to Prevent Impairment or Damage (Devices), Other systems, with specific focus on bladder irritation or discomfort.

Statistical Analysis Plan

We have estimated a necessary sample size of 56 participants per group (112 total) with an anticipated effect size of 0.52 based on expected means of 172 minutes to discharge for the experimental arm (SD 58 minutes) and 202 minutes to discharge for the control arm (SD 58 minutes), accounting for expected loss to follow up of 10%. Patients will be randomized using 14 block groups of size 8 each.

We will provide a table of demographic and clinical characteristics by assigned group. For continuous variables, we will provide means and standard deviations per group, applying a t-test

for comparison of independent means. For categorical variables, we will provide counts and percentages, applying chi-square test for comparison of proportions.

We will develop a time-to-event analysis for time to discharge including Kaplan-Meier curves by assigned group and multivariable Cox proportional hazard models.

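### One fixed, printed block size and a surgeon told every arm leave up to a third (blocks of 4) or a fifth (blocks of 8) of allocations predictable before the envelope is opened

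*Combined protocol and SAP*

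**What the plan says.** The block size is given twice. The Study Protocol section has "A randomization scheme using a block size of four will be generated". The Statistical Analysis Plan section has "Patients will be randomized using 14 block groups of size 8 each". The two must be reconciled in any case, but they share the feature at issue: one constant size, printed in the study document.

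On concealment, the Study Protocol section says "Sealed randomization envelopes will be opened for each subject after anesthesia is initiated in the operating suite". On blinding it says "This study will be single-blinded to the participant", and then "After group allocation, the surgeon will be informed of whether or not the bladder will be backfilled at the completion of the surgery".

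Neither section mentions varying block sizes, stratification, central allocation, or keeping the block size from the surgical team. Neither says who screens and consents patients, when consent is taken, how many surgeons or sites take part, or whether one list serves them all.

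**The concern.** A sealed envelope conceals the next arm only if that arm cannot be worked out from the sequence so far. With a known, constant block size and known past assignments, the last allocation in every block is certain, and earlier ones are certain whenever one arm is used up early. The surgeon learns each arm as a matter of course, because the bladder is either filled in the operating room or it is not.

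Opening the envelope after induction prevents anyone from acting on its contents. It does not prevent inference from earlier cases, and the decision to offer the trial has to come before induction. If someone with that knowledge also influenced who was offered the trial, the arms could differ in case mix. The primary outcome, time to discharge, may well depend on case mix. The baseline table and the multivariable Cox models can deal only with factors that are collected. History of bladder problems is on the list of data to be collected; position on the operating list is not.

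**Working it through.** **Inputs.** Block size 4 (Study Protocol section); 14 blocks of 8, 112 patients, 56 per group (Statistical Analysis Plan section). So allocation is 1:1 and each block is balanced.

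**The plan's own figure.** 14 × 8 = 112, which agrees with the total. 28 × 4 = 112 agrees as well, so the total does not show which size is intended.

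**Allocations known with certainty.** List every balanced sequence (6 for blocks of 4, 70 for blocks of 8). Count the positions at which one arm is already exhausted, assuming that all earlier assignments and the block boundaries are known.

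- Blocks of 4: position 3 is certain in 2 of 6 sequences and position 4 in 6 of 6. Share = (2 + 6)/(6 × 4) = 8/24 = 33.3%; 0.333 × 112 = 37.3.
- Blocks of 8: positions 5 to 8 are certain in 2, 10, 30 and 70 of 70 sequences. Share = (2 + 10 + 30 + 70)/(70 × 8) = 112/560 = 20.0%; 0.200 × 112 = 22.4.
- Both agree with the closed form 1/(b + 1) for block size 2b: 1/3 and 1/5.
- These are averages. The minimum is the last place in each block: 28 of 112 (blocks of 4) or 14 of 112 (blocks of 8).

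**Best guess.** Always guess the arm with more places left in the block; at a tie, the chance is one half.

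- Blocks of 4, averaged over positions: (1/2 + 2/3 + 2/3 + 1)/4 = 70.8%.
- Blocks of 8, by the same enumeration: 66.6%.

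**Patients already consented but not yet randomized.** The figures above describe knowledge just before an envelope is opened, with every earlier envelope open. If a decision about a patient is made while others ahead are still waiting, less is known. The documents give no backlog, so 0 to 3 is an assumed range.

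| Waiting ahead | Certain, blocks of 4 | Certain, blocks of 8 | Best guess, 4 | Best guess, 8 |
|---|---|---|---|---|
| 0 | 33.3% | 20.0% | 70.8% | 66.6% |
| 1 | 2/24 = 8.3% | 42/560 = 7.5% | 58.3% | 60.4% |
| 2 | 0% | 12/560 = 2.1% | 54.2% | 57.7% |
| 3 | 0% | 2/560 = 0.4% | 50% | 55% |

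**What it could do to the estimate (illustration only).** Assume that patients enrolled when the arm is certain differ in prognosis by 30 minutes between predicted arms. The estimated effect then shifts by 30 × 0.333 = 10 minutes (blocks of 4) or 30 × 0.20 = 6 minutes (blocks of 8), against a target difference of 30 minutes. With one patient waiting, the shift is 30 × 0.083 = 2.5 or 30 × 0.075 = 2.25 minutes. With no selection it is zero. The 30-minute gap is assumed; nothing in the documents supports a particular value.

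**After the change.** Sizes 4, 6 and 8 in random order were simulated against an observer who knows the possible sizes but not their order. About 2% of allocations are certain, and the best guess is right about 68% of the time. With sizes 4 and 6 the figures are about 5% and 69%. The list may stop inside a block at 112; an incomplete block of at most 8 can leave the arms at most 4 apart.

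**The case against.** The strongest reply is that the plan already has a real safeguard. Envelopes are sealed and opened only after anesthesia has started, so list position appears to be set in the operating suite and not at consent. A reader might infer from the arithmetic that a fifth to a third of arms are known when the next patient is enrolled. The documents do not support that: they do not say when consent is taken, and a single patient waiting brings the share to about 8%. Several surgeons who do not share assignments would also lower it. This part of the objection stands, and the larger figures are upper limits.

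A second reply is that the pathway is hypothetical, since it needs someone who tracks assignments and also influences enrolment. That stands too. A reader might infer that the trial's comparison is biased, but nothing in the documents shows it.

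A third reply is that varied blocks do not restore chance-level guessing. This is correct. A best guess near 68% is slightly worse than the 66.6% for fixed blocks of 8, so 0% certainty and 50% guessing must not be presented as the result of the change. The gain is in certainty, from 20% or 33% to about 2%.

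What the objections leave untouched is that late opening of the envelope does nothing against inference from past cases, and that the Cox models, whose covariates are not named, cannot adjust for what is not recorded.

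**Conclusion.** The point holds as an avoidable weakness in allocation concealment. Up to 33.3% of allocations with blocks of 4, or 20.0% with blocks of 8, can be known before the envelope is opened. This rests on four assumptions: one unstratified list, a team that knows every earlier assignment, knowledge of the block size and of where blocks start, and no consented patient still awaiting an envelope. With one patient waiting it is about 8%; with two it is 0% to about 2%. The documents neither confirm nor exclude these conditions. Choosing between four and eight would settle the contradiction but not this point, because either size stays fixed and printed. The change is worth making because it is cheap, not because bias has been shown.

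**What to change.** Replace both block-size sentences with one:

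> Permuted blocks of randomly varying size; the sizes and the list are held by a person not involved in enrolment or surgery and are not disclosed to the surgical team.

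Keep the actual sizes in a restricted randomization document. Do not print example sizes in the protocol text, since that would defeat the non-disclosure. The same edit removes the conflict between four and eight.

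The cost is one sentence and a regenerated list before the first patient. If a list is already in use, the change can apply to its unused part. The arms may differ by up to about 4 patients at 112, which matters little for the comparison. It would also help to state who obtains consent and when, so that a reader can judge how much predictability remains.

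### Two avoidable bias risks: the envelope is opened before the arm is needed, and, separately, nothing keeps the arm from those who record discharge time

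*Combined protocol and SAP*

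**What the plan says.** All of this is in the Study Protocol section unless noted.

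- **When the arm is revealed:** "Sealed randomization envelopes will be opened for each subject after anesthesia is initiated in the operating suite".
- **Who is then told:** "After group allocation, the surgeon will be informed of whether or not the bladder will be backfilled at the completion of the surgery".
- **When the arm is first acted on:** in group A, 200 mL of saline "will be instilled retrograde into the bladder at the completion of surgery prior to Foley catheter removal". In group B the catheter is removed at the same point without instillation.
- **Who is blinded:** "This study will be single-blinded to the participant". No one else is mentioned.
- **Primary outcome:** the investigators "calculated an adequate sample size for our primary outcome, time to discharge, with a clinically relevant 30-minute difference".
- **Care during and after surgery:** "Information will be collected about narcotics receiving during the surgical procedure, as this may affect urinary retention rates". Also collected are "intraoperative/postoperative IV fluids, postoperative opioid use". Nothing says that this care is standardised.
- **Voiding failure:** "If a subject is unable to void, they will be admitted overnight and observed for repeat trial of voiding".
- **Blocks:** the Study Protocol gives blocks of four; the Statistical Analysis Plan gives 14 blocks of eight.

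The documents do not say who decides discharge, who records its time, or what recovery staff are told about the arm.

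**The concern.** There are two separate issues.

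(a) *During the operation.* The arm is disclosed near the start of the case but is not needed until the end. In between, staff who may know it give narcotics and fluids, and the protocol itself links narcotics to urinary retention. Recording these exposures does not stop them from being influenced.

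(b) *In recovery.* Time to discharge depends partly on staff: someone decides that the patient may leave, and someone writes down the time. The overnight-admission rule shows that a judgement about voiding also enters. If those people know the arm and act or record differently because of it, the difference goes straight into the primary outcome. The documents do not say whether acting on a known instilled volume belongs to the strategy under test or is a bias to be avoided, so a small difference would be hard to interpret.

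**Working it through.** **Part (a): sequence of events.** No arithmetic applies to the risk itself. The order is: anaesthesia begins; the envelope is opened; the surgeon is told; the operation proceeds, with narcotics and fluids; saline is or is not instilled; the catheter is removed. Nothing between the second step and the fifth depends on the arm. Opening the envelope just before the fifth step would still hide the arm through consent, enrolment and induction.

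Would later opening close the route completely? Not with fixed blocks and a surgeon who has seen earlier arms. A balanced block of four has six orderings. In AABB and BBAA the last two allocations are forced; in the other four only the last one is. That is (2×2 + 4×1) = 8 forced allocations out of 6×4 = 24, or one third. In general a block of 2m has 2m/(m+1) forced allocations on average, so a block of eight (m = 4) has 8/5 = 1.6, or 20%. These shares apply only to someone who knows the block size and the earlier arms. The documents do not say who knows the block size.

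**Part (b): illustration of size.** Inputs from the Statistical Analysis Plan: means 172 and 202 minutes, SD 58 in each arm, 56 per group including an allowance for 10% loss. The planned effect size reproduces: (202 − 172)/58 = 0.517, stated as 0.52. After 10% loss, 56 × 0.9 = 50.4, so about 50 per arm.

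Assumptions not in the documents: no true effect; a staff-driven difference d between arms; two-sided 5% test; the overnight admission rates and stay lengths below.

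For a comparison of means, SE = 58 × √(2/n).

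- n = 56: SE = 10.96 minutes, critical difference 21.7 minutes.
- n = 50: SE = 11.60 minutes, critical difference 23.0 minutes.

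The rejection probability is approximately Φ(d/SE − 1.96) + Φ(−d/SE − 1.96). For d = 10 and n = 56, d/SE = 0.912, so Φ(−1.048) + Φ(−2.872) ≈ 0.149; the t distribution gives 0.148. For d = 5 and d = 15 at n = 56 the t-test gives 0.074 and 0.274.

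The planned analysis is time-to-event, so the log-rank test was simulated as a simple stand-in for the Kaplan-Meier and Cox comparison (40,000 trials per scenario; same-day times normal, mean 202, SD 58). Admitted patients were censored after all same-day discharges, at the same admission rate in both arms. The last two rows of the table instead put overnight stays of 1,000-1,400 minutes into a t-test (20,000 trials).

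| Analysis | Admitted, each arm | n per arm | No shift | d = 10 min |
|---|---|---|---|---|
| t-test | none | 56 | 5% | 14.8% |
| t-test | none | 50 | 5% | 13.7% |
| log-rank | none | 56 | 5.5% | 13.8% |
| log-rank | 5% | 56 | 5.3% | 10.1% |
| log-rank | 5% | 50 | 5.4% | 9.3% |
| log-rank | 10% | 56 | 5.4% | 8.2% |
| log-rank | 10% | 50 | 5.4% | 8.1% |
| t-test with overnight stays | 5% | 56 | 4.7% | 5.6% |
| t-test with overnight stays | 10% | 56 | 5.0% | 5.2% |

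Counting admitted patients as discharged at 1,000-1,400 minutes in the log-rank test, instead of censoring them, changes little: 9.6% and 8.0% at n = 56 for 5% and 10% admitted.

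**The case against.** The surgeon has to know the arm to instil the saline, and participant-only blinding is openly declared. Opening the envelope after induction already protects consent and enrolment. No reason is documented why theatre staff would vary narcotics or fluids by arm. Recovery staff may have clinical reasons to know the instilled volume, and their response to it may be part of the strategy. The numbers rest on invented shifts, fall almost to the nominal level in some scenarios, give both arms the same admission rate, and so do not model a difference in who is judged unable to void. The plan names neither a log-rank test nor a t-test for the primary outcome.

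Much of this stands. The operator cannot be blinded, and the point does not ask for that. The rates show sensitivity only and have no bearing on envelope timing. What does not stand is any need for the present arrangement: nothing in the documents requires the arm to be known before the end of surgery, or requires the person recording discharge time to know it.

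A reader might go further in three ways that the text does not support:

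- *That early opening exposes the recovery unit.* It does not. The surgeon learns the arm at whatever moment the envelope is opened, so (b) would remain after (a) was fixed.
- *That recovery staff are told the arm.* The documents do not say so; they only fail to prevent it.
- *That later opening makes influence on intraoperative care impossible.* Predictable allocations within fixed blocks leave some room.

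**Conclusion.** The point holds as two independent, avoidable risks of bias, neither of them demonstrated. For (a), the timing follows directly from the text, but the documents give no basis for a magnitude. For (b), participant-only blinding leaves the recording of the primary outcome unprotected. An assumed 10-minute staff-driven difference, one third of the 30-minute target, would raise a nominal 5% error rate to about 14-15% by t-test on the planning model and about 8-14% by log-rank. It would hardly move it (5-6%) if overnight stays enter a comparison of means. These rates depend entirely on the assumed shift, admission rates and stay lengths; they do not estimate this trial's actual error rate. The changes are worth making because they cost very little and cannot be applied to patients already treated and discharged.

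**What to change.** 1. Open the envelope at the end of surgery, immediately before the backfill or catheter-removal step. This keeps concealment through consent, enrolment and induction and largely, though not fully, removes the intraoperative route. The two block sizes need to be reconciled in any case.
2. Have discharge time recorded by existing staff who are not told the arm.
3. Rewrite the blinding sentence to say who is and who is not blinded.
4. If discharge decisions are made knowing the arm, report that as a limitation of the primary outcome. A recorder who does not know the arm protects the recording, not the decision.

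Whether recovery staff should know the instilled volume is a clinical decision for the investigators, and nothing is proposed here on that.

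Cost: protocol wording, a later opening moment, saline ready in every case, and an existing staff member to note the time. No extra patients or visits are needed. Blinding in recovery may be imperfect, since early urge or voided volume could suggest the arm.

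### Allocation is opened at the start of the operation although the arms differ only at its end, so patients whose surgery rules out the comparison are already randomised

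*Combined protocol and SAP*

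**What the plan says.** The title limits the trial to outpatient laparoscopic hysterectomy. On timing, the Study Protocol states "Sealed randomization envelopes will be opened for each subject after anesthesia is initiated in the operating suite". It goes on: "After group allocation, the surgeon will be informed of whether or not the bladder will be backfilled at the completion of the surgery".

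The arms separate only at the catheter step. In group A, "sterile normal saline will be instilled retrograde into the bladder at the completion of surgery prior to Foley catheter removal". For the control arm, "If the patient is assigned to group B, the Foley catheter will be removed intraoperatively at completion of the procedure". Neither instruction carries an exception.

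The list of data to be collected, also in the Study Protocol, includes "need to go home with foley catheter, intraoperative urinary tract injury, intraoperative narcotics administration, surgical complications". These are items to record. The documents contain no eligibility criteria, no check at the end of surgery, and no rule for a patient in whom the allocated step cannot be carried out. Overnight admission is mentioned only for a subject who cannot void.

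The Statistical Analysis Plan compares time to discharge by assigned group, using Kaplan-Meier curves and Cox models. Its 10% allowance is for loss to follow-up.

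**The concern.** The whole operation lies between allocation and the first moment at which the arms differ, and events in that interval can remove the comparison for a given patient. The surgeon may not be able to backfill, the catheter may have to stay, or the patient may be admitted for a surgical reason. The plan expects to record events of this kind but does not say how they bear on the allocated step or on the analysis.

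That leaves two outcomes, neither of them good. Kept in the assigned group, such patients contribute discharge times that the bladder procedure did not or could not influence, and so pull the arms together. Removed after allocation, they may be removed by someone who already knows the arm, which risks selection bias as well as lost numbers. The present timing creates this choice needlessly, because nobody needs the allocation until just before catheter removal.

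**Working it through.** **Inputs from the documents.** Target: "time to discharge, with a clinically relevant 30-minute difference" (Study Protocol). Means of 172 and 202 minutes, SD 58 in each arm, 56 per group and 10% loss (Statistical Analysis Plan).

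**Assumptions.** Two-sided alpha 0.05, since the plan states no alpha, sidedness or power. The share p of patients who cannot receive the contrast is not given, so I use 2% to 10%. The length of a surgical stay is not given, so I use 1,200 minutes.

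**The plan's own figures.** The effect size reproduces: (202 − 172)/58 = 0.517, stated as 0.52. The 56 per group does not follow from a two-sided test at 80% power: 2 × 58² × (1.960 + 0.842)²/30² = 58.7, so 59, and 59/0.9 gives 66. A one-sided Wilcoxon calculation at 80% power does give 50, and 50/0.9 gives 56. The 56 is therefore unexplained rather than shown to be wrong, and this point does not depend on it. For a comparison of means, two-sided power is 78.1% with 56 per group and 73.4% with 50 evaluable (56 × 0.9 = 50.4).

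**Dilution.** If a share p in both arms gets no contrast and is analysed as assigned, the expected difference is 30 × (1 − p), and the required sample size rises by 1/(1 − p)². SD is held at 58.

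| p (assumed) | Difference, min | Power, 56 per group | Power, 50 per group | Rise in required N |
|---|---|---|---|---|
| 0 | 30.0 | 78.1% | 73.4% | – |
| 2% | 29.4 | 76.5% | 71.7% | 4% |
| 5% | 28.5 | 73.9% | 69.0% | 11% |
| 10% | 27.0 | 69.3% | 64.3% | 23% |

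**Long surgical stays under the planned type of analysis.** The analysis named for time to discharge is time-to-event, so I used the log-rank test as a stand-in for the comparison of curves. Discharge times were simulated as normal, 172 against 202, SD 58, with 56 per arm. Replacing one patient in each arm with a 1,200-minute stay lowers two-sided power from about 71% to 57%. A repeat with 20,000 trials per setting gave 70% to 58%. With lognormal times the fall was smaller, from 62% to 54%. Late patients remain in every risk set and pull the hazards together, but their exact length hardly matters.

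**The case against.** **The effect size collapses.** A reader might put one 1,200-minute stay per 56 into the means calculation. The variance becomes (55/56) × 58² + (1/56)(55/56) × (1,200 − 202)² = 3,304 + 17,470 = 20,774, so the SD is 144 and the standardised effect 30/144 = 0.21 instead of 0.52. The arithmetic is right, but it describes a comparison of means. The plan analyses time to discharge by Kaplan-Meier and Cox, and its t-test sentence belongs to the table of baseline characteristics. The 0.21 should not be used.

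**The long-stay scenario is assumed.** This stands. Neither the frequency nor the length is in the documents. The planning times came from historical controls, and nothing says admitted patients were left out. As a partial answer, an SD of 58 could hold only about 58²/998² = 0.34% of 1,200-minute stays, fewer than one patient in 112; shorter stays could be included more often. The Study Protocol's opening also describes discharge from the PACU. On that reading, a transfer to a ward need not produce a 1,200-minute value.

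**The effect may be small.** At 2% the loss is under 2 percentage points of power. The formula also assumes no effect in any affected patient, whereas one admitted for an unrelated reason can still be backfilled.

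**The documents contradict themselves.** A reader might infer this from urinary tract injury appearing among the data items while catheter removal is unconditional. Recording an event does not contradict the allocation steps. What is missing is a rule linking the two.

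**Patients will be dropped after allocation.** The plan provides for no exclusion. This is a risk created by the gap, not something the plan intends.

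**Conclusion.** The point holds as a cheap improvement to the design. Certain from the text: allocation precedes the operation, the arms differ only at its end, both catheter instructions are unconditional, and no rule covers patients in whom the comparison becomes impossible.

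The size is not certain. At an assumed 2% to 10% the difference falls to between 29.4 and 27.0 minutes. One assumed 1,200-minute surgical stay per arm of 56 costs roughly 14 points of log-rank power (71% to 57%), with normal times and those stays counted as uncensored events. If such events are rare, or if transfer to a ward ends the PACU time, the loss is smaller.

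A reader might also infer that moving the allocation would remove long stays from the trial. It would not. Admissions for failure to void arise after any end-of-surgery check, are related to the outcome, and rightly stay in the analysis. How they are handled is a separate question.

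**What to change.** Open the envelope at completion of surgery, immediately before the catheter step. First record that both arms' procedures and same-day discharge remain possible, against criteria the investigators define in advance; which surgical findings count is for them to decide. Randomise only patients who pass, log consented patients who are not randomised with reasons, and carry the unopened envelope to the next patient so that the sequence stays intact.

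Separately, reconcile the unconditional catheter-removal step with the intraoperative events the plan expects to record, so that it is clear what the protocol intends for those patients.

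The cost is protocol wording and a short checklist. A few more patients must be consented, but the randomised total stays at 112. The result then applies to the slightly narrower group still suitable for both arms at the end of surgery. The check also adds a point of judgement before allocation. With small blocks (four in the Study Protocol, eight in the Statistical Analysis Plan) and a surgeon who learns each allocation, later assignments can sometimes be guessed. The check must therefore be recorded before opening.

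If the present timing is kept, the minimum is to prespecify analysis of all patients as randomised, state how those who cannot receive the allocated step are handled, and inflate the sample size by 1/(1 − p)² for a stated p.
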